We first proposed this study in 2005. Since then the (IMPORT- High) study is being planned in the UK to test whether a higher tumour bed dose reduces local recurrence in high risk patients. However, our study is unique in terms of the localisation and timing of delivery of tumour bed boost and may achieve a better tumour control because of the reasons explained above. The Milan group is now planning to test whether intraoperative boost using the ELIOT technique may yield superior outcome. The ELIOT technique could in theory suffer from the problem that the high dose of radiotherapy (20Gy) is delivered in a very short time (2-4 minutes) and the long term cosmetic or toxicity of such an approach is not yet known. The longer duration (25-30 min) of radiotherapy during the TARGIT intra-operative procedure, in theory, would allow for repair of DNA damage by normal tissues (but not tumour cells), thus reducing long term toxicity. This theoretical concept has been vindicated by our long term toxicity and local recurrence outcome data. Hence the TARGIT-B trial remains unique and will address a very important question and could potentially provide a better clinical outcome.

7. Trial objectives and purpose

This is a randomised controlled trial that compares two treatments in patients with early breast cancer

who have undergone local excision of a breast cancer and face a relatively higher risk of local

recurrence. The conventional policy for such a patient is to receive radiation boost to the tumour bed

delivered by external beam radiotherapy (EBRT) in addition to whole breast EBRT according to local

treatment guidelines. The experimental policy is to give targeted intra-operative radiotherapy

(TARGIT-Boost) in a single dose to substitute for the usual boost dose.

Primary Objective: To evaluate whether a tumour bed boost in the form of a single fraction of

radiotherapy given intra-operatively and targeted to the tissues at the highest risk of local recurrence

is superior (in terms of local tumour control) to standard post-operative external beam radiotherapy

boost, after breast conserving surgery in women undergoing breast conserving therapy who have a

higher risk of local recurrence.

Secondary Objectives: To compare the treatment arms with respect to site of relapse within the breast;

relapse-free survival and overall survival (breast cancer and non-breast cancer deaths –such as cardiac

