cannot be ascribed to the first or second breast tumour for instance, they do need to be treated and

intraoperative treatment may be particularly suitable. The trial will only assess these patients for

ipsilateral local control and their data will be censored for other endpoint assessments.

Changes to protocol

Protocol v2.0 included entry into the trial after the initial surgery was performed. However, at the

first trial steering committee meeting it was decided that this mode of entry was not desirable and

should be removed from the protocol based on the findings of the TARGIT-A trial – which found

that when given as a delayed procedure, TARGIT does not appear to be as effective as when it is

given concurrently with lumpectomy ¹⁵. It has also been found that progesterone receptor status

predicts the response to radiation. Therefore, there will be no stratification as per timing of

TARGIT B Protocol IRAS No: 77045 randomisation with respect to lumpectomy ¹⁵. Instead, we shall stratify as per hormone receptor status (see Table) ¹⁶. This is based on the finding in the TARGIT-A trial that progesterone receptor status appears to be the only factor that predicts the efficacy of TARGIT. The eligibility criteria will also be simplified as it will not include positive margin at first excision as an entry criterion. Therefore, randomisation will be stratified according to participating site as well as by the hormone receptor status. These changes have been incorporated into Protocol v3.0.

Protocol v4.0 included that a 'minimum' of Five "pilot" cases (non-randomised patients suitable to receive TARGIT) will be performed followed by an audit by a member of the Steering Committee (or an appointed delegate). Also, patients will be issued with a participant card so that patients can provide this card whenever they are asked about what type or how much radiation treatment they have received.

Stratification by hormone receptor status

		Tumour ER status					
		ER	ER	ER			
		positive	negative	unknown*			
Tumoum DoD	PgR positive	Stratum 1	Stratum 4	Stratum 0			
Tumour PgR	PgR negative	Stratum 2	Stratum 4	Stratum 0			
status	PgR unknown	Stratum 3	Stratum 4	Stratum 0			

Stratum 0: ER unknown

[figure not shown]
Stratum 1: ER positive, PgR positive
Stratum 2: ER positive, PgR negative
Stratum 3: ER positive, PgR unknown
Stratum 4: ER negative, (any PgR status)

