Protocol v5.0 allows the inclusion of 'no ink on margin' as a definition of 'free margin', as this is the new standard increasingly accepted around the world, and for fine needle aspiration cytology (FNAC) as part of triple assessment, in those sites where it is a long standing local practice that is not practically possible to change. Tumour grade and ER status from the cytology specimen will be used for assessing eligibility and for stratification; correlation with the final pathology will be performed at the time of analysis. Voluntary Breath Holding (VBH) or a similar technique can be used to protect the heart during whole breast external beam radiotherapy.

Each of these: the definition of free margin, use of FNAC and policy about VBH are to be recorded on the TPD of the individual site and the case record forms.

^{*} ER should be preferably known before randomisation.

Trial Schema

Outcome measures:

Local tumour control (defined as no recurrent tumour in the ipsilateral breast). Confirmation of

recurrence will follow clinical examination and core biopsy. If initial diagnosis of a local recurrence

is by using fine needle aspiration, it is necessary to confirm this diagnosis by histology of either a

therapeutic excision or a core biopsy.

Site of relapse within the breast will be recorded in order to assess whether the recurrence is at the

site of the initial tumour or at a new site and whether it has occurred within the treated field (TARGIT

or EBRT boost).

Relapse-free survival will be recorded as the time interval between randomisation and the date of

confirmation of recurrence. The actual date to be used is the clinic day on which the investigations

that led to a confirmed diagnosis of the recurrence were requested. Relapse-free survival will include

any recurrence of breast cancer or death without a prior report of relapse.

Overall survival will be the time interval between randomisation and death. We shall ascertain the

cause of death via a 'an independent cause of death committee'. Breast cancer deaths and non-breast

cancer deaths (with particular attention to deaths from cardiovascular causes and other cancers) will

be analysed in detail.

Local toxicity and morbidity will be recorded as adverse events related to the primary treatment of

the breast cancer. Quality of life will be assessed though validated patient-completed questionnaires.

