Quality of life: The primary PRO endpoint for QOL will be the FACT-B+4 trial outcome index (TOI)

score. The TOI score (0-180) is a sum of the scores of the 27 items included in the physical well-

being, functional well-being and breast cancer subscales of the FACT-B+4. A change of at least 5

points in TOI is considered to be clinically relevant or a minimally important difference (Eton et al.

2004). Secondary endpoints will be: 1) the five item arm functioning subscale score (0-20) 2) The 40

item FACT B+4 score (0-160), which reflects global quality of life including social and emotional

well-being.

Health economics: resource use, HR QOL and cost-effectiveness.

Sub-protocols

The following sub-protocols are planned for the TARGIT B Trial. Each will have their own protocol,

patient information leaflet and consent form; they have been included for completeness.

TARGIT B Protocol IRAS No: 77045 Version 6.0, Dated 10/09/2018

Page 16 of 46

A concurrent sub-protocol will assess cosmesis in a sub-set of patients. Patient's own assessment of

cosmesis will be used along with objective assessment from a frontal digital photograph. The

assessments will be made annually and assessed, blind to treatment, using specialist, validated

software (BCCT.core 2.0, INESC Porto, Portugal) which produces a composite score (Excellent,

Good, Fair, Poor) based on symmetry, colour and scar. We have used this tool already within the

TARGIT-A trial and recently presented some results ¹⁷

A patient preference subprotocol will be an interview-based determination asking patients whether

they would choose EBRT or TARGIT given hypothetical recurrence risks. This approach has been

used in the TARGIT A Trial.

A cardio-pulmonary subprotocol will assess the degree of radiotherapy-induced heart and lung

damage. The less penetrating X-rays from Intrabeam are expected to cause less damage, but this

should be formally tested.

These sub-protocols will be subject to their own sponsorship and regulatory reviews.

Assessment and follow up

The schedule for assessment and follow-up will be as follows:

Baseline (soon after surgery), pre-EBRT (around 6 months), 12, 18, 24, 30, 36, 48, 60, 72, 84, 96,

108, 120 months.

Assessment of efficacy/effectiveness:

Follow-up will be balanced between the two arms and be at least every 6 months for the first 3 years,

then annually to 10 years. Each follow up will include clinical history and examination and

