15.2. Statistical analysis

Planned Statistical Analysis: The primary endpoint is the incidence of local recurrence. All comparison will be done on an "intent to treat" basis where all randomised patients will be included in the statistical analysis. Between-treatment group comparisons of proportion of local recurrence will be compared using simple Chi-squared test. Kaplan-Meier curves and log-rank test will be used to compare the time to local recurrence in the two treatment arms. Proportional Hazard regression models will control for possible confounding variables when comparing local recurrence in the treatment groups. We will report 95% confidence intervals for all reported proportions and hazard ratios.

Interim Analysis: Interim analyses will be carried out when 41 events occur or at a median follow up of 3 years, whichever is earlier. We have chosen 3 years because it will include the peak of hazard of local recurrence. This analysis will include the assessment for the need to change the sample size, as well as futility analysis about the continuation of the trial.

In addition, analysis of data will be carried out regularly by the DMC as per MRC guidelines.

Handling of loss to follow up or missing data: In order to carry out an Intent To Treat (ITT) analysis and avoid potential bias resulting from missing data, multiple imputation methods will be used after the missingness mechanisms are established. A full report of the patterns of missing data will be reported based on the recent CONSORT guidelines²⁹. Sensitivity analysis will be carried out and reported.

Planned subgroup analyses: This will include immediate vs. delayed boost (as a second procedure), pre- vs post- menopausal chemotherapy vs. no chemotherapy, neo-adjuvant vs. other, ER, PgR, HER2 status, Oncotype DX score. Further factors will be decided before unblinding of the data.

16. Compliance and withdrawal

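### Kaplan-Meier curves for local recurrence, an endpoint that excludes death, modestly overstate the incidence named as primary; report cumulative incidence beside the planned tests

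*Protocol*

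**What the plan says.** Section 15.2 states: "The primary endpoint is the incidence of local recurrence". It then plans two comparisons of that endpoint. The first is on simple proportions: "Between-treatment group comparisons of proportion of local recurrence will be compared using simple Chi-squared test". The second is on time to event: "Kaplan-Meier curves and log-rank test will be used to compare the time to local recurrence in the two treatment arms". Proportional hazards models follow, and 95% confidence intervals are promised for reported proportions and hazard ratios.

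Section 8 (Outcome measures) defines the endpoint without death: "Local tumour control (defined as no recurrent tumour in the ipsilateral breast". Section 14.1 likewise limits local recurrence to recurrence in the ipsilateral breast. Death counts as an event only in relapse-free survival, a secondary endpoint, which covers "any recurrence of breast cancer or death without a prior report of relapse".

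The only explicit censoring rule is in Section 8 (Core Protocol). It concerns women with a metachronous cancer, who are assessed only for "ipsilateral local control and their data will be censored for other endpoint assessments". Nothing is said about deaths without local recurrence, and no competing-risk method is named.

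Section 15.1 powers the trial on a 5-year recurrence rate. Section 8 (Assessment of efficacy/effectiveness) sets visits at least every six months for three years and "then annually to 10 years". Deaths are of interest in themselves: Section 7 lists "relapse-free survival and overall survival (breast cancer and non-breast cancer deaths", with cardiac and other-cancer deaths as examples, among the secondary comparisons.

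**The concern.** A woman who dies without a local recurrence can no longer have one. Kaplan-Meier for time to local recurrence has only two outcomes, event or censored, so with death outside the endpoint she is in effect censored at death. One minus Kaplan-Meier then estimates recurrence as if nobody died first. That is a legitimate quantity, but it is not the incidence that Section 15.2 names as primary, and it lies above that incidence by an amount that grows as deaths accumulate.

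What is at stake is the absolute rate. Section 6 reads the pilot through a 5-year Kaplan-Meier rate and converts an absolute reduction of 2.74 points in local recurrence into a mortality benefit of at least 0.7%. Results are therefore likely to be read on the absolute scale, where the choice of estimator matters.

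**Working it through.** **The plan's own figure first.** Section 15.1 compares 5.64% with 2.9%, two-sided alpha 0.05, power 80%. The usual two-proportion formula with pooled variance and no continuity correction is

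n per arm = [1.960·√(2p̄q̄) + 0.842·√(p1q1 + p2q2)]² / (p1 − p2)²

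With p1 = 0.0564, p2 = 0.029 and p̄ = 0.0427 this gives about 853.5 per arm. That is 1707 in total, or 1708 after rounding each arm up, against 1707 stated. Dividing by 0.95 for 5% attrition gives about 1797, against 1796 stated. The sample size reproduces, and nothing below changes it.

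**Inputs for the check.**
- Recurrence at 5 years: 5.64% (control) and 2.9% (experimental), from Section 15.1, read here as Kaplan-Meier rates.
- Death without local recurrence by 5 years: not in the protocol. Assumed range 2% to 20%, with 5% to 10% as the main case, equal in both arms.
- Constant, independent hazards over the 5 years: an assumption.

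**Formulas.** Recurrence hazard h = −ln(1 − rate)/5 and death hazard m = −ln(1 − deaths)/5.
- 1 − KM at T = 1 − exp(−hT)
- Cumulative incidence at T = h/(h + m) × [1 − exp(−(h + m)T)]

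**Example, control arm, 5% deaths.** 5h = −ln(0.9436) = 0.0581 and 5m = −ln(0.95) = 0.0513. Cumulative incidence = 0.0581/0.1093 × (1 − 0.9436 × 0.95) = 0.531 × 0.1036 = 5.50%.

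**Results at 5 years.**

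| Assumed deaths by 5 years | Control: 1 − KM | Control: cumulative incidence | Gap (points) | Experimental: 1 − KM | Experimental: cumulative incidence | Difference between arms, cumulative incidence (KM: 2.74) |
|---|---|---|---|---|---|---|
| 2% | 5.64% | 5.58% | 0.06 | 2.90% | 2.87% | 2.71 |
| 5% | 5.64% | 5.50% | 0.14 | 2.90% | 2.83% | 2.67 |
| 10% | 5.64% | 5.36% | 0.28 | 2.90% | 2.75% | 2.60 |
| 20% | 5.64% | 5.06% | 0.58 | 2.90% | 2.60% | 2.46 |

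The ratio between arms is 0.514 on either scale.

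**Unequal mortality.** Suppose 10% die in the control arm and 5% in the experimental arm. The Kaplan-Meier difference stays at 2.74 points, because 1 − KM depends only on h. The difference in actual incidence is 5.36 − 2.83 = 2.53 points. Now suppose the recurrence hazards are identical (5.64% by Kaplan-Meier in both arms) and deaths are 5% and 10%. Kaplan-Meier shows no difference, while cumulative incidence shows 5.50% and 5.36%.

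**Ten years.** A constant hazard would give 1 − 0.9436² = 10.96% by Kaplan-Meier. With 5% to 10% deaths by 5 years continuing at the same rate, cumulative incidence would be 10.43% to 9.90%, a gap of 0.53 to 1.06 points. This is illustrative only, because Section 15.1 says the hazard peaks between 2 and 3 years. The boost-arm figures cited there for patients under 41 are 9.5% at 5 years and 13.5% at 10, whereas a constant hazard would give 1 − 0.905² = 18.1%.

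**Does the simple proportion supply the rate instead?** Section 9 expects about 250 patients a year after the first year, and 1796/250 is about 7 years. Follow-up will therefore be staggered. Unless every woman has 5 years of follow-up at analysis, the crude proportion is not a 5-year rate.

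**The case against.** The strongest case on the other side has five parts.

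- **Different questions.** The objective is superiority in local tumour control. For that, the Kaplan-Meier scale is defensible: it is not moved by mortality, whereas cumulative incidence can make the arm with more deaths look better locally. This stands, and it is why the cause-specific comparison should remain and why cumulative incidence must be read with mortality by arm. It does not make 1 − KM an estimate of the incidence that Section 15.2 names.
- **Censoring at death is inferred.** The protocol does not state it, and a statistical analysis plan, not available for this review, may deal with it. This is true. But the protocol itself pairs this endpoint with this method, and plain Kaplan-Meier offers no other treatment of such deaths. Its wording should agree with whatever the analysis plan says.
- **Kaplan-Meier is not the only summary.** The chi-squared comparison of all randomised women keeps deaths in the denominator. This is also true, but with staggered follow-up it does not replace a 5-year rate.
- **Comparability.** The pilot rate of 2.1% in women under 50, from which the 2.9% was built, is a Kaplan-Meier figure. This is a good reason to keep Kaplan-Meier rates as a supplement.
- **Size.** At 5 years the gap of 0.14 to 0.28 points is small beside sampling error: 1.96 × √(0.0564 × 0.9436/898) is about 1.5 points for one arm. This stands and limits the point to a minor one. The gap is, however, systematic and not random, and it grows with follow-up.

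**Conclusion.** The point holds as a minor matter of reporting. Kaplan-Meier is matched to an endpoint described as incidence, and the direction of the gap is certain wherever deaths without local recurrence occur. At 5 years the control-arm overstatement is about 0.14 to 0.28 points on assumed mortality of 5% to 10%, with constant independent hazards. The document gives no mortality figure, and Section 9 excludes women with severe concomitant disease that may limit life expectancy, so the size could be smaller.

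A reader might infer three stronger conclusions, which the protocol does not support:
- **That unequal deaths bias the Kaplan-Meier comparison.** They do not bias its estimate of the recurrence hazard under independent hazards. They only make the Kaplan-Meier difference depart from the difference in actual incidence.
- **That 10-year rates will be overstated by about a point.** Ten years is the length of follow-up; the protocol promises no 10-year rate. The arithmetic behind such a figure needs a constant hazard, which does not fit the protocol's own description.
- **That the tests or the sample size are at fault.** The log-rank test and Cox model remain valid for the cause-specific hazard, and the sample size stands as calculated.

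**What to change.** Amend Section 15.2 so that absolute local recurrence curves, the 5-year rate and any later rates are reported as cumulative incidence (Aalen-Johansen), with death without local recurrence as a competing event and 95% confidence intervals. State that the log-rank test and Cox model compare cause-specific hazards, with such deaths censored, and keep them for the treatment comparison. Show mortality by arm alongside, so that a lower cumulative incidence is not mistaken for better local control when it reflects more deaths. Kaplan-Meier rates may be kept as a supplement for comparison with the pilot.

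The cost is a change of wording and one extra set of estimates. No new data, visits or patients are needed: Section 14.2 already requires the date and cause of every death. The planned tests, the hazard ratio and the sample size do not change.

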Randomisation schedules will be prepared using a bespoke SAS program, blocked and stratified by centre and stratum, with equal allocation between treatment arms, by the Trials Operations Office. The schedules will be accessible by authorised staff only. Requests for randomisation can be made by either fax (receipt of a completed inclusion/exclusion criteria checklist) or telephone. A trained member of staff will confirm eligibility and perform the randomisation, according to the Standard Operating Procedure. The turnaround time for faxed randomisations is next working day, for telephone randomisations immediate provided the call is made between 09.00 and 17.30 UK time.

The randomisation codes will be included in the data sent to the Trial Statistician for analysis.

13. Blinding & other measures taken to avoid bias

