15.1. Sample size calculation

In the Oxford overview of December 2005 ²⁵ of 10 BCS trials that started in 1995, patients who were node positive had a local recurrence rate of 11%. In the more recent EORTC trial, the boost arm ^{2 26-28} had a local recurrence rate for patients <41 at 5 yrs of 9.5% and at 10 years of 13.5% and for patients 41-50, 8.7% at 10 years. Although the overall 10-year local recurrence rate was 6.2%, the recurrences were "concentrated" in the younger patients. Furthermore, the trial population was at low risk of recurrence- most tumours were <2cm and 91.9% were node negative. On the other hand, the TARGIT-B trial will focus on patients aged 45 or less, or with adverse features. Considering that local recurrence rates are reducing substantially with modern systemic therapy, we have estimated that the local recurrence rate in the conventional arm will be 5.64%.

[figure not shown]
In the long term results of our pilot series of 299 patients which received the proposed experimental treatment had even higher risk tumours (29% node positive vs. 20% node positive in the overview), but had the actuarial 5 year local recurrence rate of 1.73% ¹¹ ¹², which was about half of the expected recurrence rate in this unselected group of patients. In women <50, this study had a local recurrence of 2.1% (SE 1.5). Thus we shall take the conservative estimate of 2.9% (2.1+0.5xSE=2.9%) as the expected recurrence in the experimental arm.

Therefore, the study will be powered to detect a difference between 5.64% and 2.9% (OR=0.5, exponential hazard rate of 0.80) and will need 1707 patients. (Two sided RCT with alpha=0.05 and power=80%. Assuming an attrition of 5%, we shall aim towards an accrual goal of 1796 patients, i.e., a sample size of 898 in each group.

The study is powered for a 5 year- recurrence rate. The hazard of local recurrence peaks between 2-3 years hence we have chosen the 3-year time point for the interim analysis. An interim analysis will be performed at a median follow up of 3 years, or after 41 events, whichever is earlier. At this point may revise the sample size by considering both efficacy and futility analysis. The DMC will of course regularly review the data for both safety and efficacy as per MRC guidelines.

Using Lan-DeMets Alpha spending function with O'Brien-Fleming Boundary to reject null hypothesis.

Cumulative Patient Accrual	Alpha Spent			
~1000 (41 events)	0.003			
1796	0.035			

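### For the primary between-arm comparison, the blanket 95% interval rule in 15.2 does not match the group-sequential rejection levels in 15.1; the gap is material at the interim and small at the end

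*Protocol*

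**What the plan says.** Section 15.1 of the protocol gives the design as "Two sided RCT with alpha=0.05 and power=80"% and says that "the study will be powered to detect a difference between 5.64% and 2.9"%. It continues: "The study is powered for a 5 year- recurrence rate". On timing it says: "An interim analysis will be performed at a median follow up of 3 years, or after 41 events, whichever is earlier". The rejection rule follows, beginning "Using Lan-DeMets Alpha spending function with" and naming an O'Brien-Fleming boundary. Its table lists 0.003 at about 1000 patients (41 events) and 0.035 at 1796 patients.

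Section 15.2 describes the chi-squared, log-rank and proportional-hazards analyses and ends that paragraph with "We will report 95% confidence intervals for all reported proportions and hazard ratios". It makes no exception for the primary contrast or for the interim look. Section 17.1 says that the trial has no formal stopping rules.

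**The concern.** A confidence interval and a test of the same effect agree only when the interval's level is one minus the test's nominal level. Here the test level changes between looks and the interval level does not. For the primary comparison, the interval can therefore exclude no effect while the boundary has not been crossed.

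This matters most at the interim. Section 15.1 lets efficacy, futility and sample size be reconsidered there, and section 17.1 leaves stopping to judgement. A committee that reads the interval directly would be using a looser criterion than the boundary. If the trial stops at that look, the published effect would also be the unadjusted estimate, which is selected for being extreme.

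**Working it through.** **Inputs.** Section 15.1: 5.64% and 2.9% at 5 years; two-sided 0.05 and 80% power; interim at 41 events with 0.003; 0.035 at 1796. Section 12: equal allocation. Section 15.2: 95% intervals.

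**The plan's own sample size.** Two proportions, no continuity correction, mean rate 0.0427:
- n per arm = [1.960 × √(2 × 0.0427 × 0.9573) + 0.842 × √(0.0564 × 0.9436 + 0.029 × 0.971)]² / 0.0274² = 853.5, so 1707 in total. This agrees with the protocol.
- 1707 / 0.95 = 1796.8, against the stated 1796.

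**Design hazard ratio.** ln(1 − 0.029) / ln(1 − 0.0564) = 0.507. The protocol also prints an exponential hazard rate of 0.80. That is not the ratio implied by these two rates, and I do not use it.

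**The interim level.** O'Brien-Fleming-type spending at 0.025 per side and half the information gives 0.00305, which matches 0.003. Half the information at 41 events implies 82 final events. With the events expected from the design rates, the spending at 41 events would differ:
- 1796 × 0.0427 ≈ 77 final events: 0.0043.
- 1707 × 0.0427 ≈ 73 final events: 0.0056.

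The calculations below use 0.003 as printed.

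**Interim thresholds.** SE(log HR) = 2/√41 = 0.312.
- The 95% interval excludes 1 when HR < exp(−1.960 × 0.312) = 0.542.
- The test at 0.003 rejects when HR < exp(−2.968 × 0.312) = 0.396. At that edge the 95% interval is 0.21 to 0.73.

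**Chance of a mismatch at the interim.** At HR 0.507 the mean z is 0.679 / 0.312 = 2.175.
- P(1.960 < Z < 2.968) = 0.37.
- P(Z > 2.968) = 0.21.
- With no effect, the mismatch probability is 0.05 − 0.003 = 0.047.

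At the design effect, the mismatch is thus likelier than crossing the boundary.

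**After an early stop at HR 0.507.** The median z given Z > 2.968 corresponds to an HR of 0.34. Conditional coverage is P(2.968 < Z < 2.175 + 1.960) / P(Z > 2.968) = 0.88.

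**Coverage of the ordinary 95% interval** (simulation, 41 then 77 events, stopping when 0.003 is crossed):

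| True HR | Chance of early stop | Coverage given early stop | Coverage over both looks |
|---|---|---|---|
| 1 | 0.3% | 0% | 94.9% |
| 0.7 | 3.4% | 26% | 93.6% |
| 0.507 | 21% | 88% | 94.8% |
| 0.35 | 65% | 96% | 95.1% |

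**Final analysis** (77 events, SE = 2/√77 = 0.228). The 95% interval excludes 1 below HR 0.640.
- If 0.035 is the nominal level, rejection needs HR below 0.618. The mismatch is 3.8% at the design HR (3.4% with 82 events, 4.1% with 73) and 1.5% with no effect.
- If the nominal level is 0.049, which is what overall 0.05 with 0.003 spent at half information gives, rejection needs HR below 0.638. The mismatch is 0.2% at the design HR and 0.1% with no effect.

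**Width of a matched interval relative to 95%.** Interim at 0.003: 2.968 / 1.960 = 1.51 times. Final at 0.035: 1.08 times. Final at 0.049: 1.004 times.

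**The case against.** The strongest reply is that the 95% sentence closes the paragraph on the planned analysis and comes before a separate interim paragraph that does not mention intervals, so it may be meant for final reporting only. Section 13.1 also restricts release of outcome summaries, so few people would see an interim interval, and the data monitoring committee has the boundary in front of it. Ordinary 95% intervals beside sequential tests are common, and adjusted estimates are often left to an analysis plan, which is not shown here.

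Part of this stands. It limits who could be misled, and it makes the point a minor one. But the sentence covers all reported hazard ratios without exception. If the trial stops at the interim, that analysis becomes the reported one. An analysis plan that used another level for the primary effect would contradict the protocol.

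Four stronger readings are tempting, and the protocol does not support them:
- **That every interval is at the wrong level.** Single-arm proportions and secondary or subgroup hazard ratios are not tested against the boundary, so 95% is not inconsistent for them.
- **That the false-positive rate is inflated.** With no effect, a 95% interval would exclude 1 at one look or the other 8.3% of the time (half the information at the interim). Rejection is governed by the boundary, however, so 8.3% is not this trial's error rate.
- **That 95% intervals are generally too narrow after an early stop.** Coverage over the whole design holds at about 94–95%. Conditional coverage varies with the true effect, and the main cause of any loss is overestimation, not width.
- **That an interval for the absolute difference is excluded.** Section 15.2 does not mention one, but that is detail an analysis plan can supply.

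**Conclusion.** The point holds for the primary between-arm comparison only. The interval rule and the rejection rule disagree. At 41 events the gap is between HR 0.54 and 0.40, with a 37% chance of falling in it at the design effect. After an early stop (21% chance at the design effect), the unadjusted result is too favourable: median HR 0.34 against 0.51, with 88% coverage. At the end, the size depends on what 0.035 means: 3–4% if it is the nominal level, about 0.2% if the nominal level is about 0.049.

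These figures rest on a normal approximation for the log hazard ratio, a look at exactly 41 events, 73 to 82 final events, and stopping whenever 0.003 is crossed. Section 17.1 does not commit to that last step, and it needs reconciling with the boundary in 15.1. The chi-squared comparison of proportions was not modelled separately. This is a worthwhile improvement to reporting and does not threaten the validity of the test.

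**What to change.** Amend the sentence in 15.2 to this effect: the primary between-arm effect is reported with a confidence interval at one minus the nominal significance level in force at that look, derived from the spending function and the information actually observed; if the trial stops at the interim, a stage-wise adjusted estimate and interval are also given; 95% intervals, labelled descriptive, are used for single-arm proportions and for secondary and subgroup quantities.

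Do not write 99.7% into the text. The look is triggered by median follow-up or 41 events, whichever comes first, so it may come with fewer events. With 82 final events, a look at 30 events would spend about 0.0004, which means a 99.96% interval.

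The change affects analysis and reporting only: a sentence or two of wording, plus standard group-sequential software. The price is a wider and less favourable primary interval, about 1.5 times as wide at an interim tested at 0.003 and 1.004 to 1.08 times as wide at the end. The 0.035 entry should be corrected separately. Doing so settles the final level but does not remove the interim mismatch.
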